IMP	investigational medicinal product
IRB	institutional review board
ITP	immune thrombocytopenia
IV	intravenous
IVIg	intravenous immunoglobulin
JAK	Janus kinase
MedDRA	Medical Dictionary for Regulatory Activities
MFI	Multidimensional Fatigue Inventory
NCI	National Cancer Institute
NCS	Nerve conduction studies
NSAID	non-steroidal anti-inflammatory drug
OLE	open-label extension
OSS	ocular staining score
PASS	patient acceptable symptom state
PCR	polymerase chain reaction
PD	pharmacodynamic(s)
PGA	patient global assessment
PI	principal investigator

Abbreviation	Expansion
PK	pharmacokinetic(s)
PMDA	Pharmaceuticals and Medical Devices Agency
pSS	primary Sjögren’s syndrome
PT	preferred term
QW	once weekly
Q2W	every 2 weeks
RF	rheumatoid factor
SAE	serious adverse event
SAP	statistical analysis plan
SC	subcutaneous
SCIg	subcutaneous immunoglobulin
SF-36	36-Item Short Form Survey
SFV	safety follow-up visit
SGUS	salivary gland ultrasonography
SoA	schedule of activities
SOC	system organ class
SS-A	Sjögren’s syndrome–related antigen A
SS-B	Sjögren’s syndrome–related antigen B
STAR	Sjögren’s Tool for Assessing Response
SUSAR	suspected unexpected serious adverse reaction
SWSF	stimulated whole salivary flow
TEAE	treatment-emergent adverse event
UWSF	unstimulated whole salivary flow
VAS	visual analog scale
WOCBP	women of childbearing potential

Definitions of Terms

Term	Definition
Nonresponder	Participant who does not have a reduction in ClinESSDAI score of ≥ 3 points and/or a change in score that alters their disease severity category
Responder	Participant who has a reduction in ClinESSDAI score of ≥ 3 points and/or a change in score that reclassifies their disease from moderate severity to mild severity
Therapeutic failure	Participant who are nonresponder at week 24. This participant will discontinue study treatment

1. PROTOCOL SUMMARY

1.1. Synopsis

Protocol Title:

Open-Label Extension Study to Evaluate the Safety of Efgartigimod in Adult Patients With Primary Sjögren’s Syndrome (pSS) who Complete Qualifying Efgartigimod pSS Studies

Rationale: Efgartigimod contributes to successfully treat pSS and has the potential to improve disease manifestations by the reduction of IgG autoantibodies in pSS. This open-label extension study will evaluate the long-term safety of efgartigimod in participants with pSS who have completed the treatment period of the qualifying efgartigimod studies (including ARGX-113-2106).

Objectives, Endpoints, and Estimands:

Objectives	Endpoints
Primary	

 To evaluate the long-term safety of efgartigimod in patients with pSS 	
 Incidence and severity of AEs and AESIs, incidence SAEs, changes in laboratory test results, vital signs, and ECG results
Secondary	

 To evaluate effect and assess long-term data on durability of CRESS response 	
 Proportion of CRESS responders on ≥ 3 of 5 items at weeks 24 and 48. The 5 items are: 
 Systemic disease activity: clinESSDAI Patient-reported symptoms: ESSPRI Tear gland function: Schirmer’s test and OSS Salivary gland function: UWSF rate and SGUS Serology: serum IgG and/or RF

 To evaluate the effect of efgartigimod on clinical efficacy parameters 	
 Proportion of participants with minimal clinically important improvement from baseline in ESSDAI: improvement of ≥ 3 points in ESSDAI score at weeks 24 and 48 Proportion of participants with low disease activity: ESSDAI score of < 5 at weeks 24 and 48 Proportion of participants with minimal clinically important improvement from baseline in clinESSDAI: improvement of ≥ 3 points in clinESSDAI score at weeks 24 and 48 Proportion of participants with low disease activity: clinESSDAI score of < 5 at weeks 24 and 48

Objectives	Endpoints
	
 • Proportion of participants with minimal clinically important improvement from baseline in ESSPRI: decrease of 1 point or $\geq 15\%$ at weeks 24 and 48 • Change from baseline in ESSDAI score at weeks 24 and 48 • Change from baseline in clinESSDAI score at weeks 24 and 48 • Change from baseline in ESSPRI score at weeks 24 and 48

 • To evaluate the effect of efgartigimod on STAR 	
 • Proportion of STAR responders (score of ≥ 5) at weeks 24 and 48 when compared to baseline

 • To assess the PD effect of efgartigimod 	
 • Values, changes from baseline, and percent reduction from baseline in total IgG levels in serum over the 48-week treatment period • Values, changes from baseline, and percent reduction from baseline in autoantibodies in serum over the 48-week treatment period: 
 – Anti-Ro/SS A – Anti-La/SS B

 • To assess the exposure to efgartigimod 	
 • Efgartigimod serum concentrations over the 48-week treatment period

 • To assess the immunogenicity of efgartigimod 	
 • Incidence and prevalence of ADA against efgartigimod over the 48-week treatment period

ADA = antidrug antibody; AESI = adverse event of special interest; clinESSDAI = clinical EULAR Sjögren’s syndrome disease activity index; CRESS = Composite of Relevant Endpoints for Sjögren’s Syndrome; ECG = electrocardiogram; ESSDAI = EULAR Sjögren’s syndrome disease activity index; ESSPRI = EULAR Sjögren’s Syndrome Patient-Reported Index; IFN = interferon; IgG = immunoglobulin G; RF = rheumatoid factor; IV = intravenous; OSS = ocular staining score; PD = pharmacodynamic(s); PK = pharmacokinetic(s); pSS = primary Sjögren’s syndrome; PT = preferred term; SAE = serious adverse event; SGUS = salivary gland ultrasonography; SOC = system organ class; STAR = Sjögren’s Tool for Assessing Response; TEAE = treatment-emergent adverse event; UWSF = unstimulated whole salivary flow; VAS = visual analog scale.

No estimands have been defined for this study.

Overall Design:

ARGX-113-2211 is a long-term, single-arm, open-label, multicenter extension study of the pSS-qualifying efgartigimod studies designed to evaluate the long-term safety of efgartigimod in adult patients with pSS. Participants will be enrolled from both active and placebo arms of qualifying efgartigimod studies and receive efgartigimod 10 mg/kg over 48 weeks in the extension study without knowledge of their treatment assignment in the qualifying study. Eligible participants must have completed the treatment period of the qualifying study and must not have permanently discontinued the IMP in that study.

Brief Summary:

Participants will receive efgartigimod 10 mg/kg by IV infusion either Q2W or QW. The dosing regimen is based on whether the participant is a responder or nonresponder. Responder status will be determined by clinESSDAI assessments conducted on day 1, week 16, and week 24 and using the baseline of the qualifying study. Participants who are not responders at week 24 will be evaluated by PI for therapeutic failure. If a participant is a therapeutic failure, they will discontinue study treatment. If a participant is not a therapeutic failure, they will continue QW dosing regimen, and a clinESSDAI will be conducted at weeks 32, 36, 40, and 44 until confirming responder status and switching to Q2W dosing regimen. The PI will continue to evaluate the participant for therapeutic failure.

The study's primary objective is to assess the long-term safety of efgartigimod in participants with pSS. Additional assessments will be conducted, and blood samples collected to assess the effectiveness of efgartigimod at treating pSS, the PD effect of efgartigimod, and the immunogenicity of efgartigimod. Blood samples will also be collected to monitor the concentration of efgartigimod in blood over time.

Number of Participants:

Up to approximately 30 subjects who have completed the efgartigimod pSS study (ARGX-113-2106) will be enrolled for in the OLE study (ARGX-113-2211).

Note: *Enrolled* means the participant agrees to participate in the clinical study by completing the informed consent process.

[figure not shown]
Study Arms and Duration:

Each participant will participate in the following study periods:

- Treatment period: 48-week treatment period in which participants will receive efgartigimod doses either QW or Q2W based on their responder status. Switch points (ie, time points when clinESSDAI is conducted to determine responder status) will occur on day 1, week 16, and week 24. A participant who is not a responder on week 24 and classified by the PI as a nontherapeutic failure will continue QW dosing regimen until confirming the responder status. The participant will begin Q2W dosing regimen upon confirmation of the responder status
- 56-day follow-up period starting after the final IMP administration

Data Monitoring/Other Committee: No

1.2. Schema

Abbreviations: D = day; IV = intravenous; QW = once weekly; Q2W = every 2 weeks; Wk = week.

^a QW or Q2W dosing regimen depending on responder status. Responders (defined as participants with a decrease in clinESSDAI of ≥ 3 points from baseline of qualifying study or who have a change clinESSDAI score that reclassifies their disease from moderate severity to mild severity) will be switched from QW to Q2W dosing regimen. Nonresponders will remain on QW dosing regimen. Switch points (ie, timepoints where clinESSDAI are conducted to determine responder status) will occur on day 1, week 16, and week 24. If a participant is not a responder at week 24, they will be evaluated by the PI for therapeutic failure. If not considered a therapeutic failure, the participant will continue QW dosing regimen and will return at weeks 32, 36, 40 and 44 for a clinESSDAI assessment until confirming the responder status and switching to Q2W dosing regimen or PI considers the participant to be a therapeutic failure. For QW regimen, the final dose will be administered at week 47. For Q2W regimen, the final dose will be administered at week 46.

1.3. Schedule of Activities

Table 1: Schedule of Activities

	BL ^a	Study week																EDV ^b	SFV ^c
		1	2	3	4	5-7	8	9-11	12	13-15	16	17-23	24	25-35	36	37-47	48		
Study day (±2)	1	8	15	22	29	36-50	57	64-78	85	92-120	127	134-162	169	176-246	253	260-330	337		393
Note: All activities (safety and efficacy assessments, predose blood sampling) will be completed before administering the IMP infusion.																			
Visits that must be attended at the site are BL, W1 (for QW regimen), W2, W4, W8, W12, W16, W24, W36, W48, EDV, and SFV. Additionally, participants must attend visits at the site for their first 3 doses of efgartigimod in this OLE study. All other visits may be conducted by home health care service or telemedicine visit.																			
Informed consent	X																		
Eligibility check	X																		
Brief physical examination (symptom driven)	X ^d				X		X		X		X		X		X		X	X	X
Vital signs ^e	X				X		X		X		X		X		X		X	X	X
ECG	X				X		X		X		X		X		X		X	X	X
Glandular function																			
UWSE/SWSF	X										X		X		X		X	X	
Schirmer's test	X										X		X		X		X	X	

	BL ^a	Study week																EDV ^b	SFV ^c
		1	2	3	4	5-7	8	9-11	12	13-15	16	17-23	24	25-35	36	37-47	48		
Study day (±2)	1	8	15	22	29	36-50	57	64-78	85	92-120	127	134-162	169	176-246	253	260-330	337		393
OSS	X										X		X		X		X	X	
SGUS	X										X		X		X		X	X	
Safety laboratory assessments																			
Clinical laboratory tests (hematology and chemistry)	X				X		X		X		X		X		X		X	X	X
Urinalysis	X										X		X		X		X	X	X
Urine pregnancy testing	X																	X	X
Blood sampling																			
CCI																			
PK ^h	X ⁱ				X		X		X		X ⁱ		X		X		X		
Total IgG ^f	X				X		X		X		X		X		X		X		X
RF ^f	X				X						X		X		X		X		X
Anti-Ro/SS-A, anti-La/SS-B autoantibodies ^f	X				X		X		X		X		X		X		X		X

	BL ^a	Study week																EDV ^b	SFV ^c
		1	2	3	4	5-7	8	9-11	12	13-15	16	17-23	24	25-35	36	37-47	48		
Study day (±2)	1	8	15	22	29	36-50	57	64-78	85	92-120	127	134-162	169	176-246	253	260-330	337		393
Immunogenicity ^f	X		X		X		X		X		X		X		X		X		X
Systemic disease activity																			
ESSDAI ^f	X										X		X		X		X		
clinESSDAI	X										X		X	W32 ^k	X ^k	W40, W44 ^k	X		
Patient-reported outcome questionnaires^l																			
ESSPRI	X										X		X		X		X		
MFI	X										X		X		X		X		
PGA	X										X		X		X		X		
SF-36	X										X		X		X		X		
EQ-5D-5L	X										X		X		X		X		
PASS	X												X				X		
IMP infusion ^m	X ⁿ	X ^{o,p}																	
AE review	Continuous monitoring																		
Concomitant medications review	Continuous monitoring																		

	BL ^a	Study week																EDV ^b	SFV ^c
		1	2	3	4	5-7	8	9-11	12	13-15	16	17-23	24	25-35	36	37-47	48		
Study day (±2)	1	8	15	22	29	36-50	57	64-78	85	92-120	127	134-162	169	176-246	253	260-330	337		393

BL = baseline; clinESSDAI = clinical; ESSDAI; D = day; d/c = discontinuation; ECG = electrocardiogram; EDV = early discontinuation visit; ESSDAI = EULAR Sjögren’s syndrome disease activity index; ESSPRI = EULAR Sjögren’s Syndrome Patient-Reported Index; EULAR = European Alliance of Associations for Rheumatology; ICF = informed consent form; IgG = immunoglobulin G; IMP = investigational medicinal product; IV = intravenous; MFI = Multidimensional Fatigue Inventory; NA = not applicable; OSS = ocular staining score; PASS = patient acceptable symptom state; PCR = polymerase chain reaction; PD = pharmacodynamics; PGA = patient global assessment; PK = pharmacokinetics; RF = rheumatoid factor; SCR = screening; SFV = safety follow-up visit; SF-36 = 36-Item Short Form Survey; SGUS = salivary gland ultrasonography; SS-A = Sjögren’s syndrome-related antigen A; SS-B = Sjögren’s syndrome-related antigen B; SWSF = stimulated whole salivary flow; UWSF = unstimulated whole salivary flow; W = week.

^a BL will coincide with the final visit of a previous qualifying study. Grayed-out assessments may be conducted as part of the previous qualifying pSS studies.

^b The EDV will be performed within 7 days after last dose administration.

^c Participants will attend a safety follow-up visit 56 ± 3 days after the final IMP administration.

^d Weight mandatory at baseline.

^e Vital signs will be measured before collecting any blood sample or administering IMP infusions.

^f On IMP administration visits, blood samples must be collected predose (preferably within 2 hours before the infusion). On other visits, a blood sample may be collected at any time during the visit.

^h On IMP administration visits, blood samples for PK analyses will be collected predose (preferably within 2 hours before IMP administration). On other visits, a blood sample may be collected at any time during the visit.

ⁱ A PK sample will also be collected within 30 minutes after the end of IMP infusion.

^j The biological domain will remain blinded until the parent study is unblinded.

^k ClinESSDAI will only be conducted at weeks 32, 36, 40, and 44 if the participant is a nonresponder at week 24 and not considered a therapeutic failure by the PI.

^l The questionnaires should be performed before other study interventions and can be done one day in advance.

	BL ^a	Study week																EDV ^b	SFV ^c
		1	2	3	4	5-7	8	9-11	12	13-15	16	17-23	24	25-35	36	37-47	48		
Study day (±2)	1	8	15	22	29	36-50	57	64-78	85	92-120	127	134-162	169	176-246	253	260-330	337		393

^m The maximum total efgartigimod dose per efgartigimod IV infusion is 1200 mg for participants weighing ≥ 120 kg. The IMP weight-based dose will be recalculated if a participant’s weight has changed (increased or decreased) by more than 10% from OLE baseline (ie, weight prior to IMP infusion on day 1 of the ARGX-113-2211 study).

ⁿ The IMP infusion on day 1 will occur following eligibility check, informed consent signature, and baseline assessments.

^o Responders will reduce dosing frequency from QW to Q2W dosing regimen. Nonresponders will remain on QW dosing regimen. Switch points will occur at baseline, week 16, and week 24. The PI will evaluate a participant who is not a responder at week 24 for therapeutic failure. If the participant is not considered a therapeutic failure, QW dosing regimen will be continued, and the participant will return at weeks 32, 36, 40, and 44 for a clinESSDAI assessment up to confirming the responder status and switching to Q2W dosing regimen or if the PI considers the participant to be a therapeutic failure. For QW regimen, the final dose will be administrated at week 47. For Q2W regimen, the final dose will be administered at week 46.

^p If a participant who has reduced dosing frequency to Q2W considers their condition worsening, an unscheduled visit will occur during which a clinESSDAI and blood sampling for PK and ADA will be conducted. The participant will revert to QW dosing regimen for the remainder of the treatment period if there has been an increase in clinESSDAI score of ≥ 3 points and/or a change in score that reclassifies their disease from mild severity (clinESSDAI < 5) to moderate severity (clinESSDAI ≥ 5).

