8. STUDY ASSESSMENTS AND PROCEDURES

Study procedures and their timing are summarized in the SoA (Section 1.3). Protocol waivers or exemptions are not allowed.

Adherence to the study design requirements, including those specified in the SoA, is required for study conduct.

All baseline evaluations must be completed and reviewed to confirm that participants meet all eligibility criteria before first dose.

Operational considerations due to the COVID-19 pandemic are provided in Section 10.5.

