3.3. Schedule of Events

Schedule of events can be found in [Section 1.3](#) of the protocol.

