6. GENERAL CONSIDERATIONS

6.1. Reference Start Date and Study Day

Study Day will be calculated from the reference start date and will be used to show start/stop day of assessments and events. It will appear in every listing where an assessment date or event date appears.

Reference start date is defined as the day of the first dose of IMP.

- If the date of the event is on or after the reference start date, then:
 - Study Day = (date of event – reference start date) + 1.
- If the date of the event is prior to the reference start date, then:
 - Study Day = (date of event – reference start date).

In the situation where the event date is partial or missing, the date will appear partial or missing in the listings.

Study Day

Date implies a complete date having day, month, and year available. Unless otherwise specified, the study day will remain missing when it cannot be calculated due to absence or incompleteness of the concerned and/or reference dates.

In case the participant never received IMP, the date/time of enrolled will be used instead of first IMP administration date/time.

End of study (EOS) is defined as date of participant's last visit. A participant will have completed the study if the SFV assessments have been completed.

End of treatment (EOT) is defined as date of treatment completion or date of permanent discontinuation of IMP.

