6.3. Windowing Conventions

All assessments, including unscheduled assessments, will be allocated to an analysis visit window. Tables and listings will be based on analysis windows defined below. Allocations of assessments will be performed using their relative day.

Table B: Non-efficacy Analysis Visit Definition (immunogenicity)

Phase	Target Day	Assigned Study Day		Week Assigned
		Assigned (Inclusive) From	To	
Treatment	Not applicable ^a			Baseline
	15	1 ^a	22	Week 2
	29	23	43	Week 4
	57	44	71	Week 8
	85	72	99	Week 12
	113	100	141	Week 16
	169	142	211	Week 24
	253	212	295	Week 36
	337	296	Up to the date of SFV.	Week 48
Safety Follow-up	NA	NA	NA	SFV

confidential and proprietary to IQVIA Holdings Inc. and its subsidiaries. Unauthorized use, disclosure or reproduction is strictly prohibited.

^a Last available non-missing measurement from the parent study ARGX-113-2106.

For QW regimen, the final dose will be administrated at week 47. For Q2W regimen, the final dose will be administered at week 46.

After treatment period ends, safety follow-up will be approximately 7 weeks (56 days ± 3 days) will be summarized separately.

[figure not shown]
The above [Table B](#) contains visit window for every assessment's visited (e.g., Immunogenicity). Refer to respective visit window table for other assessments.

Some parameters which are not collected at every visit, visit window will be combined (by extending window with previous or subsequent visits).

[figure not shown]
For e.g. Week 2 are not protocol scheduled visit for brief physical examination (symptom driven), vital signs, electrocardiogram (ECG), clinical laboratory assessments, total IgG, anti-Ro/SS-A, anti-La/SS-B autoantibodies. Hence, visit window can be combined with baseline and week 4. The non-missing value closest to the target day will be used in the analysis in case of multiple observations.

Table B: Non-efficacy Analysis Visit Definition for brief physical examination (symptom driven), vital signs, electrocardiogram (ECG), clinical laboratory assessments, total IgG, anti-Ro/SS-A, anti-La/SS-B autoantibodies.

Phase	Target Day	Assigned Study Day (Inclusive)		Week Assigned
		From	To	
Treatment	Not applicable ^a			Baseline
	29	2	43	Week 4
	57	44	71	Week 8
	85	72	99	Week 12
	113	100	141	Week 16
	169	142	211	Week 24
	253	212	295	Week 36
	337	296	Up to the date of SFV.	Week 48
Safety Follow-up	NA	NA	NA	SFV

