Copyright © 2009, 2010, 2012, 2016, 2018, 2019, 2021, 2024 IQVIA. All rights reserved. The contents of this document are confidential and proprietary to IQVIA Holdings Inc. and its subsidiaries. Unauthorized use, disclosure or reproduction is strictly prohibited.

For Urinalysis, we do not have week 2, week 4, week 8, week 12 visit, as in that case the following window:

[figure not shown]
Table B: Non-efficacy Analysis Visit Definition for Urinalysis.

Phase	Target Day	Assigned Study Day (Inclusive)		Week Assigned
		From	To	
Treatment	Not applicable ^a			Baseline
	113	2	141	Week 16
	169	142	211	Week 24
	253	212	295	Week 36
	337	296	Up to the date of SFV.	Week 48
Safety Follow-up	NA	NA	NA	SFV

For Urine pregnancy testing, we only have Baseline, and Safety Follow-up schedules the following window:

Table B: Non-efficacy Analysis Visit Definition for Urine Pregnancy testing.

Phase	Target Day	Assigned Study Day (Inclusive)	Week Assigned
-------	------------	--------------------------------	---------------

Copyright © 2009, 2010, 2012, 2016, 2018, 2019, 2021, 2024 IQVIA. All rights reserved. The contents of this document are confidential and proprietary to IQVIA Holdings Inc. and its subsidiaries. Unauthorized use, disclosure or reproduction is strictly prohibited.

		From	To	
Treatment	Not applicable ^a			Baseline
Safety Follow-up	NA	NA	NA	SFV

^a Last available non-missing measurement from the parent study ARGX-113-2106.

[figure not shown]
For efficacy assessments (e.g., ClinESSDAI), wider window will be considered as follows:

Table C: Efficacy Analysis Visit Definition for ClinESSDAI.

Target Day	Assigned Study Day (Inclusive)		Week Assigned
	From	To	
Not applicable ^a			Baseline
113	2	141	Week 16
169	142	197	Week 24
225	198	239	Week 32
253	240	267	Week 36
281	268	295	Week 40
309	296	323	Week 44
337	324	Until study discontinuation	Week 48

^a Last available non-missing measurement from the parent study ARGX-113-2106.

Note: ClinESSDAI will only be conducted at weeks 32, 36, 40, and 44 if the participant is a non-responder at week 24 and not considered a therapeutic failure by the PI.

Copyright © 2009, 2010, 2012, 2016, 2018, 2019, 2021, 2024 IQVIA. All rights reserved. The contents of this document are confidential and proprietary to IQVIA Holdings Inc. and its subsidiaries. Unauthorized use, disclosure or reproduction is strictly prohibited.

a Last available non-missing measurement from the parent study ARGX-113-2106.

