18. PHARMACOKINETIC ANALYSIS

PK analyses will be performed in the PKAS.

At IMP administration visits, PK blood samples will be collected predose (within the 2 hours before IMP infusion) and post-dose (within 30 minutes after the end of IMP infusion) at baseline and week 16.

A listing of PK blood sample collection times, derived sampling time deviations, and concentrations will be provided. A subject listing of all concentration-time data will be presented by study day and scheduled time point.

Serum concentrations will be summarized using descriptive statistics for efgartigimod. The pharmacokineticist will determine a strategy for dealing with data affected by protocol deviations or events which may impact the quality of PK concentration data on a case-by-case basis with input from the study physician, as needed. Examples of protocol deviations or events include, but may not be limited to the following:

- When a predose sample is taken after IMP administration.
- Postdose samples are collected following the occurrence of incomplete or incorrect dosing for the most recent prior dose administration.
- Any event related to sample collection, handling and storage that affects the integrity of the samples and/or the bioanalytical results.
- When predose PK samples are taken outside the visit windows.
 - The study visit windows are ± 2 days

In the case of an important protocol deviation or event, the PK data collected may be excluded from the summaries

and a reason for the exclusion of the data point will be added in the appropriate listing.
The strategy for the population PK analysis and any related exposure-response modeling utilizing the efgartigimod concentration and IgG data collected from this study will be outlined separately in the PK analysis plan.

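### The schedule of activities puts the week 16 switch visit on study day 127, which is week 18 by its own count; the SAP uses day 113

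*Protocol*

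**What the plan says.** **Protocol, Section 1.3, Table 1.** The study-day row carries a ±2-day window. For the columns headed weeks 13-15, 16, 17-23 and 24 it reads "92-120 127 134-162 169". Every repeat of the header row shows the same figures.

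**Protocol, Section 1.3, footnote o.** On dosing frequency: "Switch points will occur at baseline, week 16, and week 24". Week 16 is also on the list of visits that must take place at the site.

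**Protocol, Section 8.** "Adherence to the study design requirements, including those specified in the SoA, is required for study conduct".

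**SAP, Section 6.3.** The week 16 target is day 113 throughout. The Table B row for immunogenicity gives target, from, to and label as "113 100 141 Week 16", and the row for laboratory tests, vital signs, ECG and IgG is the same. The Table C row for clinESSDAI gives "113 2 141 Week 16".

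**SAP, Section 3.3.** For the visit schedule the SAP refers back to protocol Section 1.3 ("Schedule of events can be found in"). Its list of changes from the protocol (Section 3.4) mentions only biomarker data.

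**The concern.** The week label and the day number in one column of the schedule disagree by two weeks, and the SAP agrees with the label. The column is not a routine one. At week 16 the clinESSDAI decides whether a participant on QW moves to Q2W, and it is the only post-baseline visit with a scheduled post-infusion PK sample (Protocol Section 8.5).

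A site that books by printed study day and a site that books by week number would take the same dosing decision about two weeks apart, and each could say it followed the schedule. A visit on the true week 16 day would be a deviation on paper, because it falls before the printed window opens. It would also sit in the printed column for weeks 13-15, where no efficacy assessments are planned and home visits are allowed.

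Data labelled week 16 could therefore mix weeks 16 and 18. These data feed the week 16 summaries of ESSDAI, clinESSDAI, ESSPRI and STAR (SAP Sections 13.1.5 and 13.1.6). The planned interim analysis is also triggered by completion of week 16 (SAP Section 4.2).

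**Working it through.** **Rule of the row.** Baseline is day 1 and weeks 1 to 4 are days 8, 15, 22 and 29, so day = 7 × week + 1. Against all 16 post-baseline columns, 13 fit exactly, including week 12 (85), week 24 (169), week 36 (253) and week 48 (337). Three adjacent columns do not:

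| Weeks | Printed days | 7 × week + 1 | Weekly slots printed | Weeks labelled |
|---|---|---|---|---|
| 13-15 | 92-120 | 92-106 | 5 | 3 |
| 16 | 127 | 113 | 1 | 1 |
| 17-23 | 134-162 | 120-162 | 5 | 7 |

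**Which week is day 127?** (127 − 1)/7 = 18.0. For the SAP target, (113 − 1)/7 = 16.0. The discrepancy is 127 − 113 = 14 days.

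**Is the weekly grid itself broken?** No. Days 92 to 162 hold (162 − 92)/7 + 1 = 11 weekly slots (5 + 1 + 5), and weeks 13 to 23 are 11 weeks. Only the labels are misplaced.

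**Spacing.** As printed, week 12 to week 16 is 127 − 85 = 42 days and week 16 to week 24 is 169 − 127 = 42 days. By the rule they are 113 − 85 = 28 and 169 − 113 = 56.

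**Visit windows at ±2 days.** Printed day: 125-129. Day 113: 111-115. They share no day, and the nearest edges are 125 − 115 = 10 days apart. Day 113 itself is 125 − 113 = 12 days before the printed window opens.

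**Dosing effect.** Take a participant on QW who first qualifies for Q2W at week 16, and count infusions from day 113 to day 168:

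- Switch decided on day 113: days 113, 127, 141, 155, giving 4 infusions.
- Switch decided on day 127: days 113, 120, 127, 141, 155, giving 5 infusions.

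The difference is the 10 mg/kg infusion on day 120. Time from the switch to the week 24 assessment is 169 − 127 = 42 days (3 two-week intervals) against 169 − 113 = 56 days (4 intervals).

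**Analysis windows.** Days 111-115 and 125-129 both lie wholly inside the SAP's week 16 windows of 100-141 and 2-141.

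**The case against.** The strongest reply is that this is a typographical slip with little consequence.

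- Day 113 in the SAP is a target for allocating observations, not a booking date. The SAP nowhere prints 111-115, and its own windows hold both dates.
- Protocol Section 9.3.1 has visits recalculated from actual dates under SAP rules, and those rules assign day 127 to week 16.
- The switch rule and the list of on-site visits name week 16, so the week label can be read as the operative instruction. The intended day is easy to recover from the rest of the row.
- The dosing effect needs a participant on QW who first qualifies at week 16, at a site that books by day number. It amounts to one more dose of a regimen the protocol allows up to week 47. Planned enrolment is only about 30.
- No hypothesis is tested, and excluding off-window PK samples is discretionary.

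Most of this stands as a limit on the impact. It does not remove the conflict. The schedule's own week 16 label, under its own day count and ±2-day window, gives 111-115 without any help from the SAP. The sentence in Section 8 that makes the schedule binding does not say whether label or day number prevails, and a printed day with a window is a natural thing to book from. The documents do not show how any site actually booked.

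**Conclusion.** The concern holds. Three adjacent cells of the study-day row are wrong. The one for week 16 is off by 14 days and gives a dose-deciding visit two possible windows that do not overlap.

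The consequence is mainly operational: at most one additional infusion and 14 fewer days on Q2W before week 24, for a participant on QW who first qualifies at week 16 and whose site follows the printed day. That figure assumes infusions exactly on the weekly grid. The number of participants affected cannot be found from the documents.

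The analysis is largely protected. Week 16 observations keep their label under either date, and the secondary efficacy time points at weeks 24 and 48 are consistent. What remains is a possible mixture of two visit times in the week 16 summaries. The error should be fixed, but it does not threaten the study's main results.

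**What to change.** In every printing of the Table 1 header row, change the study-day cells to 92-106 (weeks 13-15), 113 (week 16) and 120-162 (weeks 17-23). Correcting 127 alone would leave its neighbours wrong.

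The SAP targets need no change. Once the cell reads 113, the ±2-day visit window that SAP Section 18 cites for PK samples ("The study visit windows are ± 2 days") applies to that day. No new listing is needed to see when week 16 visits took place, because SAP Section 6.1 already says of study day: "It will appear in every listing where an assessment date or event date appears".

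The cost is three table cells, with no extra visits, participants or outputs. An administrative letter or the next amendment should be enough. Protocol Section 10.1.1 requires ethics approval before changes to the study design are implemented, so the sponsor should confirm which route applies and tell sites which day to book in the meantime.
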